7.4.3. Clinical Criteria for Monitoring for Potential Hepatic Decompensation

Patients will be monitored for potential hepatic decompensation events throughout the study. Clinical criteria for monitoring these events and the interruption/discontinuation of investigational product is summarized in [Table 4](#).

Investigational product should be discontinued permanently if the patient received a liver transplant or experiences multi-organ failure as defined in Table 4, Part A. Patients should continue to return for scheduled study visits for safety follow-up.

Patients who experience other potential hepatic decompensation events defined in Table 4, Part B should be closely monitored until normalization or stabilization. Patients may be rechallenged after a minimum of 30 days if fully resolved OR stable and approved by the Medical Monitor and Investigator.

Table 4: Clinical Criteria for Monitoring Potential Hepatic Decompensation Events and Interruption / Discontinuation of Investigational Product

A. Hepatic Decompensation Events Requiring Mandatory Discontinuation of Investigational Product	
Decompensation Event	Action Taken / Rechallenging Criteria
Liver Transplant Multi-organ failure requiring hospitalization	Discontinue IP permanently and follow patients until normalization/stabilization. Continue to return for scheduled study visits for safety follow up.
B. Hepatic Decompensation Events Requiring Interruption of Investigational Product	

 • Liver failure defined as worsening synthetic function that is persistently worse relative to baseline and/or progressive over time (see Table 3, Part B)^a • Variceal bleeding or recurrent variceal bleeding^b documented by endoscopy or accompanied by anemia or melena with a hemoglobin drop of ≥ 2 g/dL • Ascites^c including: 
 ○ Worsening – requires increase in drug therapy or surgical intervention (paracentesis or shunt procedure) ○ Refractory ascites – unresponsive to medication; patient not candidate for transjugular intrahepatic portosystemic shunt (TIPS) or shunt; requires large volume paracentesis ○ Hyponatremia (≤ 125 mEq/L) secondary to ascites • Spontaneous Bacterial Peritonitis • Hepatic Encephalopathy, Grade ≥ 2 • Any liver-related event requiring hospitalization and treatment (except multi-organ failure) • Hepatorenal syndrome Type 1 or Type 2 and acute kidney injury, hepatopulmonary syndrome, or portopulmonary syndrome 	
Closely monitor until normalization or stabilization.
 
The patient may be rechallenged after a minimum of 30 days if fully resolved OR stable and approved by the Medical Monitor and Investigator
 
IP should be re-initiated at a lower dose (or lower dose frequency) and titrated per Investigator discretion.

^a Patients experiencing INR ≥ 2.0 unless due to vitamin K deficiency should be discontinued from IP permanently without rechallenge and should return for scheduled study visits for safety follow up.

^b Endoscopic confirmation of gastric or duodenal varices without evidence of bleeding should be closely monitored; investigational product may be interrupted at Investigator discretion

^c New onset ascites requiring treatment should be closely monitored; investigational product may be interrupted at Investigator discretion

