7.4.2. Liver Biochemistry Assessments for Potential Hepatic Injury or Hepatic Decompensation

[figure not shown]
Liver biochemistry will be assessed to evaluate biochemical triggers that will prompt an immediate reevaluation of patients for potential hepatic injury or hepatic decompensation. These assessments will be performed at:

- Each protocol-specified visit (Table 1)
- Unscheduled visits as needed in the event of signs or symptoms of suspected hepatic injury or decompensation or if laboratory alerts have been triggered

It is important that the laboratory assessments be completed as required and that the central laboratory be used for assessments whenever possible. In the event that a patient cannot return to the clinic for a scheduled or unscheduled visit, or there is an event that triggers a need for an immediate assessment, the use of a local lab is permissible at the discretion of the Investigator. In these cases, the Investigator will obtain the laboratory results and the laboratory normal ranges.

The process for assessing criteria is presented in Figure 2, and the specific threshold(s) for each laboratory analyte to trigger mandatory repeat testing and, potentially, a complete patient evaluation (depending on the repeat result) are summarized in Table 3.

Figure 2: DILI Management Algorithm

DILI = drug-induced liver injury; IP = Investigational Product

NOTE Other laboratory criteria include: ALT, AST, total bilirubin, INR, and electrolytes (sodium).

Table 3: Liver Laboratory Criteria for Monitoring of Suspected Hepatic Injury or Potential Hepatic Decompensation and Criteria for Interruption or Discontinuation of Investigational Product

A. Laboratory Criteria for Monitoring Suspected Hepatic Injury		
Laboratory Parameter	Action Taken	Rechallenging Criteria
Total Bilirubin		If a patient interrupts IP, they may be rechallenged after a minimum of 30 days if fully resolved OR stable and approved by the Medical Monitor and Investigator.
Baseline \leq ULN and \geq 3x baseline	Interrupt IP	
Baseline $>$ ULN and \geq 2x Baseline	Interrupt IP	
ALT or AST		
$>$ 3x baseline (and $>$ ULN)	Interrupt IP	
\geq 2x baseline	Repeat Test in 2 to 3 days, interrupt IP if still elevated	
Electrolytes^a		
Sodium $<$ 130 mEq/L	Repeat Test in 2 to 3 days, interrupt IP if still below limit	
B. Laboratory Criteria for Monitoring Potential Hepatic Decompensation (Absence of Clinical Symptoms)		

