Total Bilirubin	Closely monitor until normalization or stabilization.	The patient may be rechallenged after a minimum of 30 days if fully resolved OR stable and approved by the Medical Monitor and Investigator.
Baseline \leq ULN and 1.5 mg/dL increase from baseline	If values continue to increase relative to the baseline value, interrupt IP.	If laboratory values do not normalize, IP should not be restarted.
Baseline $>$ ULN and 1.0 mg/dL increase from baseline		
INR^b	Closely monitor until normalization or stabilization.	The patient may be rechallenged after a minimum of 30 days if fully resolved OR stable and approved by the Medical Monitor and Investigator.
$>$ 0.3 increase from baseline	If values continue to increase relative to the baseline value, interrupt IP.	If laboratory values do not normalize, IP should not be restarted.
\geq 2.0 unless due to vitamin K deficiency	Discontinue IP permanently	Continue to return for scheduled study visits for safety follow up. Monitor closely for clinical outcomes per protocol.
C. Laboratory Criteria for Monitoring Potential Hepatic Decompensation in the Presence of Clinical Symptoms		
Total bilirubin thresholds defined in Part B OR an INR increase from baseline of \geq 1.5 are observed in the presence of clinical symptoms of cholestatic hepatitis or hepatic encephalopathy ^c	Discontinue IP permanently	Continue to return for scheduled study visits for safety follow up. Monitor closely for clinical outcomes per protocol.

IP = investigational product

^a Sodium will be measured as an assessment of liver failure (hyponatremia).

^b Does not apply in patients on anti-coagulants.

^c Symptoms of cholestatic hepatitis includes dark urine and jaundice. Symptoms of hepatic encephalopathy may include lack of awareness, shortened attention span, lethargy, gross disorientation, or coma (unresponsive to verbal or noxious stimuli).

It should be noted that it is difficult to recognize every potential marker of hepatic or renal deterioration. There is no substitute for good medical judgment. Investigators will be reminded to be cautious and mindful in their evaluation of patients' symptoms, signs, and laboratory results. However, for example, a single abnormal laboratory analyte result may be artefactual; accordingly, Investigators will be allowed to implement an alternate follow-up procedure if considered appropriate based on their medical judgement, but only after documented agreement with the Sponsor's Medical Monitor.

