8.4. Dose Adjustment, Interruption, and Withdrawal from Investigational Product or Study

Investigational product may be temporarily decreased (eg, from 10 mg twice weekly to 5 mg twice weekly, or from 5 mg twice weekly to 5 mg once weekly) or temporarily or permanently stopped based on tolerability concerns. Investigational product may be resumed at the maintenance dose upon resolution of gastroenteritis or worsening renal function or dehydration if there is no evidence of liver injury. For rechallenge following all other dose interruptions (see Table 5), investigational product should be initiated at a lower dose and patients monitored more frequently with up-titration considered based on tolerability.

Adjustments, interruptions, discontinuation, and any rechallenge of investigational product should be implemented per the criteria outlined in Table 5. Patients that discontinue investigational product are expected to continue in the study (and follow the regular visit schedule, with the exception of PK sampling [trough PK may be required in the event of an AE consistent with hepatic injury or decompensation]) until the end of the study, but may withdraw consent at any time.

Table 5: Criteria for Dose Adjustment, Interruption, Discontinuation, and Rechallenge

DOSE ADJUSTMENT		
Criteria	Action Taken with IP	Adjustment
New Onset Severe Pruritus	Drug holiday or less frequent dosing	Return to original dose regimen if tolerated
DOSE INTERRUPTION		
Criteria	Action Taken with IP^a	Rechallenge^b
If liver biochemistries indicative of suspected hepatic injury are identified as exceeding upper threshold criteria and require immediate interruption (see Part A of Table 3) ^c	Interrupt immediately upon initial observation	Patient may be rechallenged after a minimum of 30 days if fully resolved OR stable and approved by the Medical Monitor and Investigator.
Other liver biochemistries indicative of suspected hepatic injury are outside upper threshold criteria upon repeat testing as defined in Part A of Table 3 ^d	Interrupt after confirmation by repeat testing	
Liver biochemistries indicative of potential hepatic decompensation in the absence of symptoms (see Part B of Table 3) ^e	Closely monitor until normalization or stabilization. If values continue to increase relative to the baseline value, interrupt	

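### The protocol does not say consistently whether investigational product is interrupted when bilirubin or INR rises past the Table 3 Part B trigger and then plateaus

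*Protocol*

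**What the plan says.** **Table 3 Part B (Section 7.4.2)** covers laboratory changes without clinical symptoms. For bilirubin the trigger is a rise of 1.5 mg/dL when baseline is at or below ULN; when baseline is above it, the table reads "ULN and 1.0 mg/dL increase from baseline". For INR the trigger is more than "0.3 increase from baseline", not applied to patients on anticoagulants. The first action is "Closely monitor until normalization or stabilization". Interruption is conditional: "If values continue to increase relative to the baseline value, interrupt IP". A separate INR row requires permanent discontinuation at or above "2.0 unless due to vitamin K deficiency".

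**Table 5 (Section 8.4)** repeats the conditional rule in its row for Table 3 Part B.

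**Table 4 Part B (Section 7.4.3)** is headed as a list of decompensation events that require interruption. Its first entry is "Liver failure defined as worsening synthetic function that is persistently worse relative to baseline and/or progressive over time", followed by a pointer to Table 3 Part B. Its action cell uses the same monitoring words as Table 3 Part B. It then allows rechallenge after at least 30 days and says product is to be re-initiated at a lower dose or frequency.

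**Section 7.4.3 text and the Table 5 row for Table 4 Part B** say to monitor and do not say to interrupt. That Table 5 row nevertheless sits in the block headed as dose interruption.

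**The concern.** The entry for liver failure joins persistence and progression with and/or, so persistence alone can qualify. The only operational criterion it gives is the pointer to Table 3 Part B, where persistence alone does not lead to interruption. An asymptomatic value that crosses the trigger and then holds steady therefore falls within both tables, and neither says which governs.

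Three things are at stake:
- **Safety.** Sites could handle the same laboratory course differently in a population chosen for its hepatic impairment.
- **Exposure.** PK is a primary objective (Section 6.1). Serial sampling takes place at Weeks 12, 18, 24, 30 and 48 (Section 12.1), and PK sizing rests on about 20 OCA patients (Section 15.2). Interruption followed by a lower restart changes what those visits measure.
- **Deviations.** The PK population excludes major deviations that may affect exposure (Section 15.1). With two candidate rules, compliance in this range cannot be judged consistently.

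**Working it through.** The plan states no figure to reproduce. The check has three parts: what each place says about a plateau, whether any values fall in the overlap, and what an interruption would cost in doses.

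**1. Instruction for an asymptomatic rise that has stopped rising**

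| Place | Reading |
|---|---|
| Table 3 Part B | Monitor; interrupt only on further increase |
| Table 5, row for Table 3 Part B | Same |
| Table 4 Part B, heading | Interruption required |
| Table 4 Part B, liver-failure entry | Persistence suffices; points to Table 3 Part B |
| Table 4 Part B, action cell: monitoring sentence | Monitor |
| Table 4 Part B, action cell: rechallenge sentences | Presuppose that product was stopped |
| Section 7.4.3 text | Monitor |
| Table 5, row for Table 4 Part B | Action says monitor; block heading says interruption |

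There are two inconsistencies: between Table 3 Part B and the Table 4 Part B heading, and within Table 4 Part B itself.

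**2. Width of the overlap**

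Let b be the baseline. The lower edge is the Part B trigger, read as at least the stated bilirubin rise. The upper edge is the Table 3 Part A bilirubin limit, where interruption is immediate, or INR 2.0, where product is discontinued. The baselines are illustrative assumptions; the protocol gives no numerical ULN.

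- Bilirubin, baseline above ULN: b + 1.0 up to but not including 2b. Non-empty when b + 1.0 < 2b, that is b > 1.0 mg/dL.
  - b = 2.0: 3.0 to <4.0
  - b = 3.0: 4.0 to <6.0
  - b = 5.0: 6.0 to <10.0
- Bilirubin, baseline at or below ULN: b + 1.5 up to but not including 3b. Non-empty when b + 1.5 < 3b, that is b > 0.75 mg/dL.
  - b = 1.0: 2.5 to <3.0
- INR: above b + 0.3 and below 2.0. Non-empty when b < 1.7.
  - b = 1.2: >1.5 to <2.0
  - b = 1.5: >1.8 to <2.0

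A patient at 3.0 mg/dL who then holds 4.2 for three visits is 1.2 above baseline, past the 1.0 trigger and below the Part A limit of 6.0.

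**3. Doses at issue if the Table 4 heading governs**

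The minimum time before rechallenge is 30 days. Weekly dosing: 30/7 = 4.3, so about 4 doses. Twice weekly: 2 × 30/7 = 8.6, so at least 8 doses. A restart at a lower dose or frequency would follow.

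**The case against.** The strongest reply is that Table 4 Part B never tells the site to interrupt. Its action cell, the Section 7.4.3 text and the matching Table 5 row all say to monitor. The pointer to Table 3 Part B could also be read as importing that table's whole rule, including its condition for interruption, which would leave one rule. This stands in part: a reader might infer that the tables give flatly opposite orders, and the text does not go that far. It does not remove the problem. The Part B heading still says interruption is required, and the rechallenge and re-initiation text makes sense only if product was stopped. Footnotes b and c make interruption discretionary for lesser findings, which suggests it is not discretionary for the listed events.

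A second reply is scope: Table 3 is laboratory, Table 4 is clinical, and Table 5 keeps biochemistries and clinical events in separate rows. But the liver-failure entry names no symptom, points to the asymptomatic part of Table 3, and carries a footnote that turns on an INR value. Scope narrows the conflict without resolving it.

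Two points of wording also stand. Whether a flat plateau is still a worsening is arguable. INR fits synthetic function more directly than bilirubin, which enters only through the cross-reference.

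Finally, Section 7.4.2 lets the investigator use an alternate follow-up after documented agreement with the Medical Monitor. That limits divergence but does not say which table is the default.

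**Conclusion.** The point holds as an unresolved inconsistency in the interruption rule. It is confined to asymptomatic values between the Part B trigger and the Part A bilirubin limit or INR 2.0, with patients on anticoagulants outside the INR part. Within that range the overlap is real for ordinary illustrative baselines.

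Three stronger readings go beyond the document:
- **That Table 3 Part B orders dosing to continue.** This is inferred from the conditional interruption; the table does not say it.
- **That Table 4 prescribes about 4 weekly or 8 twice-weekly missed doses.** Those figures apply only if the heading governs over the action cell.
- **That the situation will be common.** The protocol gives no frequency for a rise followed by a plateau.

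The point should still be corrected. It concerns when study drug is stopped, in a trial whose primary objectives are PK and safety, and it leaves handling and deviation status open for the same laboratory course.

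**What to change.** Reconcile these places so that a persistent, non-progressive laboratory change falls under one stated rule:
- Table 3 Part B, action for bilirubin and INR;
- Table 4 Part B: heading, liver-failure entry, cross-reference and action cell;
- the Section 7.4.3 paragraph on Part B events;
- both Table 5 rows, for Table 3 Part B and for Table 4 Part B.

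Check Section 13.1.1.4 at the same time: the liver-failure adverse event of special interest uses nearly the same and/or definition without a numerical threshold, so its counts may vary in the same way. Which rule applies is for the sponsor's clinical team.

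The cost is a short, coordinated text amendment and a notice to sites. No new data or assessments are needed. Editing one entry or one cell would not be enough, because the mismatch inside Table 4 Part B and its echo in Table 5 would remain.

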7.4.1. Signs and Symptoms of Potential Hepatic Injury or Decompensation

Patients should be instructed to contact study personnel if they notice any of the following signs and symptoms or have healthcare interactions outside of the study setting

Signs and Symptoms of Hepatic Injury or Decompensation:

- Specific signs and symptoms of liver impairment: yellowing of the skin or the whites of eyes, pale-colored stools, urine color change from pale to deep amber [dark] (reflecting impaired bilirubin metabolism)
- More general signs and symptoms of ascites and encephalopathy: confusion, swelling of the legs or abdomen
- Non-specific signs and symptoms of impaired health: nausea, vomiting, abdominal pain, diarrhea, weight loss, fever and chills, worsening or new fatigue, weakness, loss of appetite
- Significant intercurrent illnesses such as gastroenteritis may exacerbate hepatic injury or decompensation (eg, established severe abdominal pain, vomiting, and diarrhea for more than 4 days) and should be an indication for prompt investigational product interruption and complete patient evaluation

Other Symptoms:

- Worsening of renal function or likely dehydration

Healthcare Provider (HCP) Interactions:

- Visits to primary HCP or referral to any specialist for any new symptoms (other than ongoing care for stable comorbidities)
- New medications or changes to current medications prescribed from HCP or any new over the counter medications or herbal supplements
- Laboratory procedures or assessments performed by an HCP

Signs and symptoms for potential hepatic injury or decompensation should be followed by (1) evaluation of liver biochemistry for suspected drug-induced liver injury (DILI) or potential hepatic decompensation ([Section 7.4.2](#)), (2) assessment of clinical events for potential hepatic decompensation ([Section 7.4.3](#)), (3) triggering of close monitoring or investigational product interruption/discontinuation per criteria ([Section 8.4](#)), (4) documentation in the AE eCRF or the SAE eCRFs ([Section 13.1](#)), and (5) contact with the Medical Monitor.

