Clinical events indicative of hepatic decompensation (see Part B of Table 4)	Closely monitor until normalization or stabilization	The patient may be rechallenged after a minimum of 30 days if fully resolved OR stable and approved by the Medical Monitor and Investigator. IP should be re-initiated at a lower dose (or lower dose frequency) and titrated per Investigator discretion.

Gastroenteritis (established severe abdominal pain, vomiting, diarrhea for more than 4 days)	Interrupt	If no evidence of liver injury is detected, IP may be restarted at the same dose after resolution of intercurrent illness.
Evidence of worsening of renal function or dehydration	Interrupt	
DOSE DISCONTINUATION		
Criteria	Action Taken with IP	Rechallenge
If INR increases ≥ 2.0 in absence of clinical symptoms criteria (unless due to vitamin K deficiency) ^f	Discontinue / No Rechallenge	Discontinue IP permanently and continue to return for scheduled study visits for safety follow-up. Continue to return for scheduled study visits for safety follow-up. Monitor closely for clinical outcomes according to protocol assessments.
If total bilirubin thresholds (Part B of Table 3) are observed in the presence of clinical symptoms of cholestatic hepatitis or hepatic encephalopathy ^f		
Multi-Organ failure requiring hospitalization		
Liver transplantation		
Pregnancy		

Fully resolved = Return to baseline levels or return to within normal limits (WNL). IP = investigational product

^a If patient is unable to be evaluated promptly, study drug must be immediately interrupted.

^b Requires complete documentation of complete resolution or normal/baseline results based on laboratory parameters and symptoms.

^c Total bilirubin baseline \leq ULN and $\geq 3x$ baseline, baseline $>$ ULN and $\geq 2x$ baseline, ALT or AST $> 3x$ baseline (and $>$ ULN)

^d ALT or AST $\geq 2x$ baseline or electrolytes (sodium < 130 mEq/L).

^e Total bilirubin baseline \leq ULN and 1.5 mg/dL increase from baseline OR baseline $>$ ULN and 1.0 mg/dL increase from baseline; INR > 0.3 increase from baseline

^f If INR increases ≥ 2.0 in the absence of clinical symptoms or if or total bilirubin thresholds OR an INR increase from baseline of ≥ 1.5 are observed in the presence of clinical symptoms of cholestatic hepatitis or hepatic encephalopathy.

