13.1.1.4. Adverse Events of Special Interest

The following decompensation events are adverse events of special interest; a subset of these are also captured as additional efficacy assessments (see [Section 14.2.3](#)).

- Variceal bleeding or recurrent variceal bleeding documented by endoscopy OR patient presenting with anemia or melena (hemoglobin drop ≥ 2 g/dL) and found to have varices documented by endoscopy, irrespective of hospitalization or requirement of blood transfusion.
- Gastrointestinal bleeding as a result of gastric or duodenal varices verified by endoscopy
- Hepatic encephalopathy, Grade ≥ 2
- New onset ascites requiring treatment
- Worsening of ascites (requiring increase in drug therapy or requirement of surgical procedure such as paracentesis or shunt placement)
- Refractory ascites -unresponsive to medications, and patient is not a candidate for TIPS or shunt and requires large volume paracentesis
- Hyponatremia ($\text{Na} \leq 125$ mEq/L) secondary to ascites
- Spontaneous bacterial peritonitis (confirmed by diagnostic paracentesis- by cell count/chemistry)
- Hepatorenal syndrome Type 1 and Type 2 and Acute Kidney Injury (AKI)
- Liver failure defined as worsening of liver synthetic function that is persistently worse relative to baseline and/or progressive over time:
 - Hepato-pulmonary syndrome
 - Porto-pulmonary syndrome
 - Liver Transplant
 - Increase in MELD scores by 3 points relative to baseline, persistent over time and unrelated to vitamin K deficiency related increase in INR

- Any liver related event that requires hospitalization and treatment

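### Acute kidney injury without evidence of liver injury falls under two conflicting restart rules, and the protocol does not say which governs

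*Protocol*

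**What the plan says.** Two parts of the Protocol govern restart after a renal event.

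**Section 7.4.3, Table 4 Part B.** Under the heading "B. Hepatic Decompensation Events Requiring Interruption of Investigational Product", one bullet reads "Hepatorenal syndrome Type 1 or Type 2 and acute kidney injury, hepatopulmonary syndrome, or portopulmonary syndrome". No cause or grade of kidney injury is given. Rechallenge is possible only after a minimum of 30 days, when the event has resolved or is stable, with approval from the Medical Monitor and the Investigator, and at a lower dose or dosing frequency. Table 5 in Section 8.4 carries the same rule in its row headed "Clinical events indicative of hepatic decompensation (see Part B of Table 4".

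**Section 8.4 text and Table 5 renal row.** The text says that study treatment "may be resumed at the maintenance dose upon resolution of gastroenteritis or worsening renal function or dehydration if there is no evidence of liver injury". After all other interruptions it requires a lower dose. The renal row of Table 5, which covers worsening renal function or dehydration, shares its restart cell with the gastroenteritis row: "If no evidence of liver injury is detected, IP may be restarted at the same dose after resolution of intercurrent illness". Neither place sets a minimum wait or an approval step.

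Two other sections bear on how these are read. Section 13.1.1.4 lists "Hepatorenal syndrome Type 1 and Type 2 and Acute Kidney Injury (AKI" among the decompensation events of special interest. Section 7.4.1 places "Worsening of renal function or likely dehydration" under a separate sub-heading for other symptoms.

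**The concern.** Acute kidney injury is, on its face, a worsening of renal function. When no liver injury is found, the same event meets the Table 4 Part B bullet and the Table 5 renal row, and the two prescribe different restart timing, approval and dose.

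Section 8.4 tells sites to apply Table 5, so the conflict sits inside the table they will consult. The layout makes the lenient choice easy. In Table 5 the action cell of the decompensation row speaks only of close monitoring, while the renal row says plainly to interrupt. A site looking up a rise in creatinine could reasonably stop at the renal row.

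The consequence would be an early, full-dose restart after a listed decompensation event in a Child-Pugh B or C patient, in a trial where safety is a primary objective. It could also mean different handling of the same event of special interest across the roughly 35 planned sites.

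**Working it through.** The protocol gives no figure to reproduce here. The check is a comparison of the two rules, followed by simple arithmetic on stated assumptions.

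**Rules side by side, for acute kidney injury with no evidence of liver injury**

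| | Table 4 Part B and the Table 5 decompensation row | Section 8.4 text and the Table 5 renal row |
|---|---|---|
| Minimum wait | 30 days | None; on resolution |
| Approval | Medical Monitor and Investigator | None stated |
| Restart dose | Lower dose or frequency | Same dose |

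**Where the overlap begins and ends**

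- Renal worsening short of acute kidney injury: renal row only.
- Acute kidney injury with evidence of liver injury: Part B only, because the renal row requires that no liver injury be found.
- Acute kidney injury without evidence of liver injury: both.

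The third case is not empty. The protocol separates suspected hepatic injury (Table 3 Part A) from hepatic decompensation (Table 3 Parts B and C, and Table 4), so a listed decompensation event can occur with the injury criteria unmet.

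**Size of the timing difference (hypothetical)**

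The protocol gives no recovery time. Assume recovery d days after interruption, with both rules counted from interruption. The gap is at least 30 − d days. Twice-weekly doses in the gap number (30 − d) × 2/7, and once-weekly doses (30 − d)/7.

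| d (assumed) | Gap, at least | Twice-weekly doses | Once-weekly doses |
|---|---|---|---|
| 3 | 27 days | 27 × 2/7 = 7.7 | 27/7 = 3.9 |
| 7 | 23 days | 23 × 2/7 = 6.6 | 23/7 = 3.3 |
| 14 | 16 days | 16 × 2/7 = 4.6 | 16/7 = 2.3 |

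**Size of the dose difference**

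Section 8.4 gives its example reductions as "from 10 mg twice weekly to 5 mg twice weekly, or from 5 mg twice weekly to 5 mg once weekly". In weekly terms:

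- 2 × 10 = 20 mg against 2 × 5 = 10 mg, a reduction of 50%.
- 2 × 5 = 10 mg against 1 × 5 = 5 mg, a reduction of 50%.
- On 5 mg once weekly, Table 2 names no lower regimen, so no difference can be computed.

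**The case against.** The strongest reply is that the rows are already divided by type of event. Table 4 is headed as hepatic decompensation, and its kidney-injury wording shares a bullet with hepatorenal, hepatopulmonary and portopulmonary syndromes. The Table 5 renal row shares its cell with gastroenteritis and refers to resolution of an intercurrent illness. Section 7.4.1 likewise sets renal worsening apart. On this reading, hepatorenal-type injury follows Part B and pre-renal injury from an intercurrent illness follows the renal row. That may well be what was intended, but no passage says so. The sentence in the Section 8.4 text carries no intercurrent-illness condition, Section 13.1.1.4 lists acute kidney injury as a decompensation event without limiting it to the hepatorenal type, and nowhere is the investigator asked to attribute the injury.

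A second reply is that the renal row is only permissive, so a site that waits and restarts lower breaches nothing. That is true, but nothing directs the site to the stricter rule, and one that uses the express permission would contravene Part B. The Section 8.4 clause on all other interruptions does not settle it either, since an interruption for a Part B event is itself one of those others.

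A third reply points to safeguards. Section 7.4.1 sends signs of decompensation to Section 7.4.3 before Section 8.4, although whether that sequence reaches the other-symptoms item is arguable. Section 7.6 requires discussion of suspected decompensation with the Medical Monitor and contact at least every 2 weeks after interruption. Table 5 footnote b requires documented resolution. These reduce the risk, but none fixes the wait, the dose or the restart approval.

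It stands that the recovery times above are assumed, that the frequency of the event is unknown, and that no endpoint or analysis rule is directly affected.

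**Conclusion.** The concern holds. For acute kidney injury without evidence of liver injury, the protocol states two restart rules that disagree on timing, approval and dose, and it gives no precedence. This is a conflict between stated instructions, not detail left for another document.

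The disagreement over approval and same versus lower dose comes directly from the text. The halving of the weekly dose rests on the step-downs named in Section 8.4 and applies only to the two twice-weekly regimens. The gap of 16 to 27 days rests on assumed recovery at 14 to 3 days and on counting the 30 days from interruption, a starting point that Part B does not state. How many patients would be affected cannot be estimated from the protocol.

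The point should be corrected, because it concerns a named safety event in a high-risk population. Confidence is medium, because a split between decompensation and intercurrent illness is a plausible unstated intent.

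**What to change.** In the Section 8.4 text and the Table 5 renal row, limit same-dose restart to worsening renal function or dehydration that does not meet criteria for acute kidney injury or hepatorenal syndrome and shows no evidence of liver injury. Add that any event listed in Table 4 Part B, acute kidney injury included, follows the Part B restart rule.

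If the sponsor's clinicians prefer pre-renal acute kidney injury to stay under the same-dose rule, narrow the Table 4 Part B bullet to hepatorenal-type injury instead. Either choice removes the conflict.

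The cost is amendment wording. Under the first option, some patients with quickly reversible pre-renal injury would wait longer and restart at a lower dose.
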